4.1.1.3. DLT-Equivalent Toxicities

A DLT-equivalent toxicity (ET) is an AE that meets the DLT criteria as defined above and occurs in any cycle other than the DLT assessment period for cohorts in Phase 1a (42 days for Cohorts A1-A6 and B1-B2) and occurs in any cycle for cohorts in Phase 1b. In addition to the DLT assessment period, available safety data beyond the DLT assessment period may also be taken into consideration prior to a decision to advance to the next dose level or the determination of the RP2D.

For individuals experiencing a DLT-ET, dose modifications can be made as outlined in Section 6.6. If cumulative incidence of DLT-ET is 30% at any point during study, re-evaluation of dose will occur.

4.1.1.4. Determination of Recommended Phase 2 Dose

The RP2D will be chosen following discussion between the Lilly CRP/CRS and the investigators based on consideration of the totality of the data during interim analyses and upon completion of

Phase 1a (not inclusive of the backfill cohorts), including but not limited to LY3435151 dose adjustments, AEs, chronic intolerance, PK/PD data, and irAEs. All available data will be used including AEs in the short term (90 day) follow-up period. If LY3435151 has an acceptable clinical safety profile and shows sufficient activity, additional studies and/or cohorts may be added to determine a safe dose alone or in combination with other anticancer therapies. Tumor-infiltrating lymphocyte level and other biomarkers will be evaluated and may influence enrichment strategies for subsequent studies and/or cohorts.

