Abbreviations: AE = adverse event; C = Cycle; CTCAE = Common Terminology Criteria for Adverse Events; D = Day; ECG = electrocardiogram; ECHO = echocardiogram; ECOG = Eastern Cooperative Oncology Group; iRECIST = immuno-Response Evaluation Criteria in Solid Tumors; PK = pharmacokinetic; RECIST = Response Evaluation Criteria in Solid Tumors; Q3W = every 3 weeks.

Post-Treatment Follow-Up Schedule of Activities

Visit	Short-Term Follow-Up ^a			Long-Term Follow-Up ^b	Comments
	801	802	803	804-X	
Relative Day within Cycle	30-Day Follow-Up ± 5 days	60-Day Follow-Up ± 7 days	90-Day Follow-Up ± 7 days	(90 ± 14 Days)	
Physical exam	X				
Vital signs	X				Including weight, temperature, pulse rate, pulse oximetry, blood pressure, respiratory rate
ECOG performance status	X				
Radiologic imaging		X		X	Only for patients who discontinue study treatment without objectively measured progressive disease, continue to evaluate tumor response according to planned standard of care tumor assessment schedule until patient has objective disease progression or study completion.
Adverse events collection/CTCAE grading		X		X	CTCAE version 5.0. Collect AEs for 30 days following cessation of study treatment and SAEs for 90 days or 30 days following cessation of study treatment if the participant initiates new anticancer treatment, whichever comes first. Note: All pregnancies and exposure during breastfeeding must be reported, from time of treatment through 120 days following cessation of treatment, or 30 days following cessation of treatment.
Concomitant medication		X			All concomitant medications received up to 30 days after the last dose of study treatment should be recorded. Concomitant medications administered 30, 60, and 90 days after the last dose of study treatment should be recorded for SAEs and events of clinical interest.
Optional tumor biopsy	X				An optional tumor biopsy may be performed, if clinically feasible, after disease progression or at additional study time points, if warranted and agreed upon by the

Visit	Short-Term Follow-Up ^a			Long-Term Follow-Up ^b	Comments
	801	802	803	804-X	
Relative Day within Cycle	30-Day Follow-Up ± 5 days	60-Day Follow-Up ± 7 days	90-Day Follow-Up ± 7 days	(90 ± 14 Days)	
					investigator and Lilly.
Hematology	X				See Appendix 2.
Clinical chemistry	X				See Appendix 2.
Coagulation	X				PT or INR and aPTT should be collected at the mandatory Safety Follow-Up Visit after discontinuation of study therapy.

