AE collection	X	X	X	X	
Per CTCAE version 5.0. Collect AEs for 30 days following cessation of study treatment and SAEs for 90 days or 30 days following cessation of study treatment if the participant initiates new anticancer treatment, whichever comes first.
 
As part of AE/SAE collection, monitor vital signs and perform standard laboratory tests (hematology, chemistry, urinalysis, and pregnancy testing) at the same frequency as the study treatment period. All laboratory tests during the continued access period will be performed in the local laboratories only.
 
In the event of an IRR, blood samples will be collected for PK, IG, and exploratory hypersensitivity analyses at the following time points, as close as possible to: (i) the onset of the IRR, (ii) the resolution of the IRR, and (iii) 30 [±3] days following the IRR. Exploratory hypersensitivity samples may be analyzed for markers of basophil/mast cell activation (eg, tryptase), immune complex formation (eg, C3 levels) and cytokine release (eg, IL-6) as appropriate for the clinical presentation.

Administer study intervention	X				See Section 6.1 for study intervention administration details and guidelines.

Abbreviations: AE = adverse event; CTCAE = Common Terminology Criteria for Adverse Events; IG = immunoglobulin; IL = interleukin; IRR = infusion-related reaction; PK = pharmacokinetics; SAE = serious adverse event.

- ^a Continued access follow-up begins when the patient and the investigator agree that the patient will no longer continue treatment in the continued access period and lasts approximately 30 days

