6.6. Dose Modification

Dose reductions are not allowed in this study.

No dose modification for either LY3435151 or pembrolizumab (delays or omissions greater than 14 days) is allowed during the DLT observation period (42 days for Cohorts A1-A6 and B1-B2). Starting at Cycle 3, dose delays will be permitted. See Section 7 for discontinuation criteria.

After the DLT observation period, doses of the LY3435151 or pembrolizumab may be delayed, omitted, or discontinued to manage specific AEs or other toxicities. All dose modifications should be documented, including the approach taken and a clear rationale for the need for modification. The investigator must assess whether the toxicity is at least possibly due to study treatments and apply the dose modification guidelines. Investigators are encouraged to consult Lilly for additional guidance.

A cycle is defined as an interval of 21 days as shown in the SoA (Section 1.3). A delay of a cycle due to holiday, weekend, bad weather, or other unforeseen circumstances will be permitted for a maximum of 7 days and not counted as a protocol deviation. The reason for the delay should be documented on the eCRF.

Starting at Cycle 3, if a patient requires a cycle delay for any safety reasons other than those above, study treatment should be resumed within 21 days, if possible and appropriate. In rare circumstances, a cycle delay of >21 days may be permitted before permanent treatment discontinuation, as long as the patient demonstrates clinical benefit, does not have objective progression, and is recovering from the toxicity. Longer delays may be allowed for irAEs, as described in Section 6.6.1. Such circumstances must be discussed with the Lilly CRP/CRS.

Adverse events of immune-related etiology are expected because of the study drug's mechanism of action and may occur shortly after the first dose or several months after the last dose. Study treatment must be withheld if the patient experiences a drug-related toxicity or a severe or life-threatening AE.

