8.3.1. Time Period and Frequency for Collecting AE and SAE Information

Although all AEs after signing the ICF are recorded by the site in the CRF/electronic data entry, SAE reporting to Lilly begins after the patient has signed the ICF and has received study drug. However, if an SAE occurs after signing the ICF, but prior to receiving LY3435151, it needs to be reported ONLY if it is considered reasonably possibly related to study procedures.

Medical occurrences that begin before the start of study intervention but after obtaining informed consent will be recorded on the AE CRF.

All SAEs will be recorded and reported to the sponsor or designee immediately and under no circumstance should this exceed 24 hours. The investigator will submit any updated SAE data to the sponsor within 24 hours of it being available. Serious adverse events, including death, caused by disease progression should not be reported unless the investigator deems them to be possibly related to study treatment.

Investigators are not obligated to actively seek AE or SAE after conclusion of the study participation. However, if the investigator learns of any SAE, including a death, at any time after a participant has been discharged from the study, and he/she considers the event to be reasonably related to the study intervention or study participation, the investigator must promptly notify the sponsor.

Care will be taken not to introduce bias when detecting AEs and/or SAEs. Open-ended and nonleading verbal questioning of the participant and/or legal guardian is the preferred method to inquire about AE occurrences.

Refer to the SoA (Section 1.3) for the timing of AE/SAE collection.

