5.4.7. Safety Analyses

All patients who receive at least 1 dose of any study therapy will be evaluated for safety and toxicity.

Safety measures that will be used in the study include AEs, DLT (defined in protocol) in dose escalation phase, clinical laboratory test results and vital signs. The MedDRA Version 22.0 (or higher) will be used when reporting AEs by MedDRA terms. A treatment-emergent adverse event (TEAE) is defined as an event that first occurred or worsened in severity between the first dose of study treatment and 30 days after the last dose of study treatment and related serious AEs (SAEs) reported beyond 30 days after the last dose of study treatment. Immune-related adverse event (irAE) is also indicated in the database and will be summarized in the safety analysis.

Safety analyses will include summaries of the following:

- DLTs at each dose level in Part A and Part B
- AEs, including severity and possible relationship to the study drug
- DLT-equivalent AEs, including severity and possible relationship to the study drug
- SAEs, summarized by PT and repeated for events deemed by the investigator to be possibly related to study treatment

- irAEs, summarized by PT and repeated for events leading to dose delays or omissions, for events leading to discontinuations from study treatment, and for events leading to death
- AEs leading to dose delays or omissions, summarized by PT
- AEs leading to discontinuations from study treatment, summarized by PT and repeated for events deemed by the investigator to be possibly related to study treatment
- AEs leading to death, summarized by PT and repeated for events deemed by the investigator to be possibly related to study treatment
- reasons for deaths, summarized for all deaths, deaths on therapy, and deaths within 30 days of treatment discontinuation
- treatment-emergent abnormal changes in laboratory values
- treatment-emergent abnormal changes in vital signs and electrocardiograms
- Listings of all AEs, TEAEs, SAEs, and deaths will also be provided.
- Listings of all laboratory data will be provided with a flag for values outside of the laboratory normal. Abnormal results will be listed separately for all enrolled patients.

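### The RP2D decision is to use adverse events from the 90-day follow-up, but non-serious events, including immune-related ones, are scheduled for collection for only 30 days after treatment stops

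*Protocol*

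**What the plan says.** Protocol Section 4.1.1.4 describes the RP2D choice as resting on the totality of the data, names irAEs as one input, and adds: "All available data will be used including AEs in the short term (90 day) follow-up period". The amendment history (Appendix 8) attributes the text on the 90-day period to FDA feedback, so it was put there on purpose.

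The post-treatment table in Protocol Section 1.3 sets the collection rule: "Collect AEs for 30 days following cessation of study treatment and SAEs for 90 days or 30 days following cessation of study treatment", where the shorter SAE limit applies "if the participant initiates new anticancer treatment, whichever comes first". Section 8.3.1 gives no other window and defers to that table: "Refer to the SoA (Section 1.3) for the timing of AE/SAE collection".

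Protocol Section 6.6 says that immune-related events "may occur shortly after the first dose or several months after the last dose".

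SAP Section 5.4.7 defines a TEAE as an event that first occurs or worsens "between the first dose of study treatment and 30 days after the last dose of study treatment". Past that limit the definition admits one further class of event only: "and related serious AEs (SAEs) reported beyond 30 days after the last dose of study treatment". The same section plans separate summaries of SAEs and of irAEs, and listings of all AEs.

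A footnote to the continued-access table in Protocol Section 1.3 says that follow-up there "lasts approximately 30 days", although the table itself has 60- and 90-day visits.

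**The concern.** The decision rule names AEs, not only SAEs, over a 90-day period, and the collection schedule does not supply them. An irAE that is troublesome but not serious, and that begins after day 30, has no scheduled route into the database.

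This matters because late immune toxicity is a risk that the protocol itself foresees. Sections 2.3 and 6.6.1 also warn that the combination may make irAEs more frequent or more severe. Escalation cohorts are small: Section 4.1.1.1 sets a minimum of 3 evaluable patients for Cohorts A2 to A6, so one patient is a third of a minimum-size cohort. Events that were not collected cannot be recovered at analysis.

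**Working it through.** The plan has no sample-size or power figure to reproduce on this point. The check sets the stated windows side by side.

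| Window | Source | Non-serious AEs | SAEs |
|---|---|---|---|
| Named for the RP2D | Protocol 4.1.1.4 | 90 days | 90 days |
| Collected | Protocol 1.3 | 30 days | 90 days, or 30 with new anticancer treatment |
| Counted as TEAE | SAP 5.4.7 | 30 days | 30 days; later only if related |

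1. **Size of the gap.** For non-serious AEs: 90 − 30 = 60 days, and 60/90 = 67% of the follow-up period. Visits 802 (day 60) and 803 (day 90) both lie in the uncovered part. For SAEs the gap is 90 − 90 = 0 days, or 90 − 30 = 60 days once new anticancer treatment starts.

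2. **What still reaches the database after day 30.** SAEs do, subject to the new-treatment limit. Events of clinical interest (Protocol 8.3.7) may be non-serious, and Section 6.5 has concomitant medication recorded for them at 30, 60 and 90 days. That list holds only overdose without symptoms or abnormal laboratory results and one liver-test pattern, and it states no collection window. Sections 8.3 and 8.3.2 provide for follow-up of events already open. The gap therefore concerns new non-serious onsets on days 31 to 90.

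3. **Marks in the schedule.** The AE row carries marks under follow-up columns. The extracted table does not show reliably which visits they belong to. The comment beside them sets the 30- and 90-day limits in words, so I take those as governing.

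4. **Anchor dates.** Short-term follow-up starts when patient and investigator agree to stop treatment; the TEAE window runs from the last dose. If that agreement comes 0 to 21 days after the last dose (my assumption: up to one cycle), the TEAE window closes 30 − 0 = 30 to 30 − 21 = 9 days into the 90-day follow-up.

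5. **Analysis side.** The SAE and irAE summaries in SAP 5.4.7 are not restricted to TEAEs, but they state no onset window. They can show late events that were collected; they cannot show those that were not.

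**The case against.** The best defence is that Section 4.1.1.4 speaks of available data. It sets no collection window, and SAEs to day 90 are AEs, so the sentence can be met as written. That stands: this is a mismatch between intent and collection, not a strict contradiction. It does not close the gap, because the sentence says AEs, irAEs are a named input, and the non-serious ones are not scheduled for collection.

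It is also fair that many consequential late irAEs would qualify as SAEs, through hospitalization or as important medical events, and so be captured. The gap also affects only patients who stopped treatment more than 30 days before the decision.

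Four stronger readings are tempting, and the documents do not support them:

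- **DLT-equivalent toxicities are missed at every dose level.** Protocol 4.1.1.3 ties these to events in a cycle, and Section 6.6 defines a cycle as a 21-day interval. An event 31 to 90 days after treatment has stopped is not clearly a DLT-equivalent at all.
- **Late SAEs judged unrelated are lost from the primary safety endpoint.** They leave the TEAE tables only. SAP 5.4.7 summarizes SAEs separately and lists all of them, and the protocol names SAEs beside TEAEs as endpoints in both phases.
- **Two thirds of the safety information is missing.** The 67% is a share of days. Nothing in the documents says how many irAEs start in those days.
- **The continued-access footnote affects the RP2D.** Under Sections 6.7.1 and 6.7.1.1 that period begins after study completion, which follows the final analysis of the primary and secondary objectives. The footnote is an editorial inconsistency.

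**Conclusion.** The point holds as a specific shortfall in collection. Non-serious irAEs starting on days 31 to 90 are not scheduled to be recorded, apart from the narrow events-of-clinical-interest list, although the RP2D section counts on AEs from that period. For patients who start new anticancer treatment, SAE collection shortens to 30 days as well.

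The gap is 60 of 90 follow-up days for non-serious events. Its effect on the dose decision cannot be quantified, because the documents give no rate of late-onset non-serious irAEs. The conclusion assumes that the written comment in the Schedule of Activities governs collection, as Section 8.3.1 indicates. It is a worthwhile, low-cost correction, and it does not put the escalation design in doubt.

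**What to change.** - **Protocol 1.3 and 4.1.1.4:** reconcile the two by recording irAEs, serious or not, through Visit 803 at the existing 60- and 90-day contacts. Both phases already schedule PK and immunogenicity blood draws at Visits 802 and 803, so no new visit or test is needed. Say whether the new-treatment limit that applies to SAEs also applies to these irAEs. If the sponsor means only SAEs after day 30, Section 4.1.1.4 should say so, at the price of not having the non-serious events for the decision.
- **SAP 5.4.7:** state that the planned SAE and irAE summaries include onsets to day 90 whatever the investigator's attribution, presented beside the 30-day TEAE table. This sets a window for summaries already planned.
- **Editorial, separately:** align the continued-access footnote with that table's own 60- and 90-day visits.

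The cost is a short amendment and a little more case report form entry. The limit is that, without new tests, the extra contacts will mostly find events that patients report. Hematology, chemistry and thyroid tests are scheduled in follow-up only at Visit 801, so silent laboratory abnormalities after that visit would still largely go unseen.

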4.1.2. Dose Expansion Phase

[figure not shown]
For both Part A and Part B, after all patients in the dose-escalation phase have completed the DLT observation period or discontinued, an interim safety and PK/PD analysis will be conducted before opening the dose expansions. Monotherapy Cohorts (C1 and C2) can start accruing patients as soon as the Part A RP2Dm decision has been made.

In the dose expansion phase 1b, a 2-stage design with randomization will be implemented to determine the treatment for patients with immune-oncology (IO) naïve TNBC and gastric adenocarcinoma. Within each tumor type of IO naïve TNBC and gastric in the dose expansion phase, Stage 1 will enroll 16 patients to be randomized with 1:1 ratio to receive either LY3435151 monotherapy (Cohort C1 or C2) or LY3435151 and pembrolizumab combination therapy (Cohort D1 or D2). Randomization will begin after the RP2Dc has been selected and continue only until 8 patients have accrued into the C1 and C2 cohorts. At Stage 2, approximately another 32 patients in each tumor type (to a total of at least 40 patients) will be enrolled to receive LY3435151 in combination with pembrolizumab (Cohort D1 or D2). An interim data review will be performed based on safety, efficacy, and PK/PD data from the first 20 enrolled patients in combination dose expansion (including patients from both Stage 1 and Stage 2) for each tumor types of IO naïve TNBC and gastric adenocarcinoma.

[figure not shown]
Approximately 30 patients with other IO naïve tumor types will be selected for enrollment based on TIL positivity and will receive LY3435151 in combination with pembrolizumab (Cohort D3). Patients in this cohort should be tested for all biomarkers or companion diagnostic tests required to confirm that the patient is not eligible for any approved IO therapeutic drug treatment prior to being screened for eligibility to receive LY3435151 in combination with pembrolizumab based on TIL positivity.

[figure not shown]

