squamous cell carcinoma (HNSCC), squamous cervical carcinoma, high-grade serous ovarian carcinoma, hepatocellular carcinoma (HCC), undifferentiated pleomorphic sarcoma (UPS), and leiomyosarcoma (LMS).

Disclosure Statement: This is a sequential treatment study with 13 cohorts with no masking.

Number of Participants:

Approximately 170 patients with advanced solid tumors will be enrolled in this study.

- **Phase 1a:** Total enrollment will be determined by the incidence of dose-limiting toxicities (DLTs).
 - Monotherapy dose escalation (Part A): approximately 18 to 22 patients will be enrolled. An additional 12 patients in total may be enrolled at 2 selected dose levels to further inform safety, pharmacokinetics (PK), and pharmacodynamics (PD).
 - Combination dose escalation (Part B): approximately 6 to 8 patients will be enrolled.
- **Phase 1b:** Approximately 126 patients will be enrolled into Phase 1b in this study.
 - A randomization design will be applied to TNBC (C1 and D1) and gastric adenocarcinoma (including gastroesophageal junction) (C2 and D2) cohorts. For each of the 2 tumor types:
 - Stage 1: approximately 16 patients will be initially enrolled and randomized with 1:1 ratio to monotherapy dose expansion (Part C) or combination dose expansion (Part D)
 - Stage 2: additional approximately 32 patients will be enrolled to combination dose expansion (Part D). An interim data review will be performed based on safety, efficacy, and PK/PD data from the first 20 enrolled patients in combination dose expansion (including patients from both Stage 1 and Stage 2).
 - Tumor-infiltrating lymphocyte (TIL) selected cohort with multiple tumor types in combination dose expansion (D3): approximately 30 patients will be enrolled.

Intervention Groups and Duration:

Patients enrolled in this Phase 1a/1b study will receive LY3435151 monotherapy or in combination with pembrolizumab, as shown in the following table. The planned duration of treatment is not fixed; participants will remain on study until disease progression or unacceptable toxicity occurs; duration of pembrolizumab treatment will be fixed at up to 2 years. If participants are discontinued from pembrolizumab, they will be allowed to continue on LY3435151 treatment if receiving ongoing clinical benefit. Likewise, if patients are discontinued from LY3435151 treatment, they will be allowed to continue on pembrolizumab if receiving ongoing clinical benefit for up to 2 years.

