4.1.1. Dose Escalation Phase

Phase 1a (dose escalation) will assess the safety and tolerability of LY3435151 to identify a monotherapy recommended phase 2 dose (RP2D) and a combination RP2D in patients with solid tumors associated with TIL positivity:

- TNBC
- Gastric adenocarcinoma (including gastroesophageal junction)
- HNSCC
- Squamous cervical carcinoma
- High-grade serous ovarian carcinoma
- HCC
- UPS and LMS.

Patients enrolled in Part A (Cohorts A1 through A6) will receive LY3435151 monotherapy. Patients enrolled in Part B (Cohorts B1 and B2) will receive LY3435151 and pembrolizumab.

The RP2D will be determined based on the number of observed dose-limiting toxicities (DLTs) and PK/pharmacodynamic (PD) data, and may be below the maximum tolerated dose (MTD), which may not necessarily be reached during the dose escalations. The dose-escalation phase will employ a modified toxicity probability interval (mTPI-2) method and starting with Cohort A2 will enroll at least three evaluable patients per cohort. Treatment cycles will consist of 21 days. A 2-cycle DLT observation will apply to all cohorts in Phase 1a. Refer to Section 4.1.1.1 for additional details on the dose escalation method.

A minimum of 1 patient will be enrolled in Cohort A1 and will receive a 10-mg dose. If the 10-mg dose level DLT period is cleared, Cohort A2 (30-mg dose level) will be initiated.

If a patient in Cohort A1 experiences a DLT, additional patients will be enrolled into Cohort A1 following the mTPI-2 method. Based on the mTPI-2 method, at least additional 4 patients will need to be enrolled and experience no DLT during the DLT observing period before escalating to the next dose level (Cohort A2).

After the first patient in Cohort A2 receives the first dose of LY3435151, there will be a delay of 1 week before the second patient receives LY3435151 to allow for safety observation. In all subsequent cohorts, the first patient in each dose level will be observed for at least 24 hours before treatment of additional patients; no additional delays are required for subsequent patients.

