Patients in Cohorts A2, A3, A4, A5, and A6 will receive proposed doses of 30 mg, 100 mg, 300 mg, 900 mg, and 1800 mg, respectively, provided safety is established in the preceding cohorts. Once the DLT period of 42 days is completed for respective dose levels within Cohorts A1 to A6, 2 selected cohorts can be expanded with an additional 6 patients each to further inform safety, PK, and PD. For example, additional patients at dose level 5 (900 mg Q3W) may be enrolled in parallel with Cohort A6 after Cohort A5 has cleared the DLT period.

In the Combination Dose Escalation (Part B), 2 dose levels will be explored. Dose level 1 in Part B will be decided based on, but not limited to, the safety and PK/PD data from monotherapy expansion cohorts. The dose of pembrolizumab will remain constant. Once enrollment to dose level 1 in Part B begins, dose escalation will occur in parallel for both Part A and Part B. However, enrollment in a Part B cohort can begin only after all previous dose level cohorts in monotherapy and combination dose escalation (as applicable) are complete, as determined by Eli Lilly and Company (Lilly). For example, if dose level 5 900 mg Q3W is decided as the starting dose level for Part B, Cohort B1 will only begin after the safety of dose level 6 in monotherapy dose escalation is cleared, and Cohort B2 may begin only after both Cohort A6 and Cohort B1 are complete.

If safety data from Part A indicate that de-escalation of the LY3435151 dose is warranted, no additional patients will be enrolled in Treatment Part A or Treatment Part B at dose levels higher than the de-escalated dose.

Lilly and the investigators will hold a meeting to review safety and available PK/PD results after completion of the DLT period for each cohort to ensure it is safe to continue with the next dose-escalation cohort.

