6.3. Measures to Minimize Bias: Randomization and Blinding

This is an open-label study. The Phase 1b dose expansion part will implement a randomization design to mitigate the selection bias in allocating patients with TNBC or gastric adenocarcinoma to either monotherapy dose expansion (Part C) or combination therapy dose expansion (Part D) for the first 16 patients enrolled into the TNBC or into the gastric cohorts.

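### Early C1/C2 entrants can use up randomised monotherapy places, and no SAP analysis set isolates the randomised Stage 1 patients

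*Protocol*

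**What the plan says.** Protocol 4.1.2 makes four statements about how the expansion opens:

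- For both escalation parts, once all patients have finished or left the DLT period, "an interim safety and PK/PD analysis will be conducted before opening the dose expansions". Read alone, this is one gate for the whole phase.
- The sentence after it sets an earlier start for two cohorts: "Monotherapy Cohorts (C1 and C2) can start accruing patients as soon as the Part A RP2Dm decision has been made".
- Stage 1 randomises 16 patients 1:1 in each of TNBC and gastric adenocarcinoma.
- "Randomization will begin after the RP2Dc has been selected and continue only until 8 patients have accrued into the C1 and C2 cohorts".

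Protocol 6.3 says randomisation is there to limit selection bias between Part C and Part D and applies it "for the first 16 patients enrolled into the TNBC or into the gastric cohorts". Protocol 9.2 justifies n=16 per tumour type by the need to evaluate PK/PD and safety between monotherapy and combination. It builds the interim 20 from 8 Stage 1 and 12 Stage 2 patients.

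SAP 5.1.2 starts the randomised expansion after both Part A and Part B are complete. Its text does not mention early C1/C2 accrual, and it uses the same 8 + 12 split. SAP 5.4 summarises expansion data by arm within tumour type. In SAP 5.4.1 the ITT and Safety sets treat randomised and enrolled as the same thing, and the PK set is drawn from enrolled patients. No set is limited to Stage 1.

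**The concern.** There are two separate problems.

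(a) The stopping rule counts patients accrued to C1/C2, not patients randomised to them. Anyone entering between the monotherapy (RP2Dm) and combination (RP2Dc) dose decisions is non-randomised but fills one of the 8 places. A single such patient makes 4.1.2 incompatible with 6.3, and with its own statement that Stage 1 randomises 16.

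(b) Whether or not anyone enters early, the planned summaries merge the roughly 8 randomised combination patients with about 32 who enrol later without randomisation.

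At stake is the comparison that randomisation was introduced to protect. Safety is the primary objective, and a monotherapy-versus-combination difference could come from who was selected, or when, rather than from adding pembrolizumab.

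**Working it through.** **Plan's own total.** Protocol 1.1: "Approximately 126 patients will be enrolled into Phase 1b in this study". From 4.1.2 and 1.1: 2 × (16 + 32) + 30 = 126, which matches. This also settles an ambiguity in the stopping rule. If 8 meant C1 and C2 together, the total would be 8 + 2 × 40 + 30 = 118, so 8 must be per cohort.

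**Effect of early entry.** Let k be the early C1 (or C2) entrants per tumour type. The documents do not give it, so the range is 0 to 8. Randomisation stops after 8−k further monotherapy allocations at probability 0.5, so the expected number randomised is (8−k)/0.5 = 2(8−k), of whom 8−k receive the combination. The randomised share of 40 combination patients is (8−k)/40, and the interim 20 splits (8−k)/(12+k).

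| k | Expected randomised | Monotherapy arm not randomised | Randomised share of 40 | Interim split (Stage 1/Stage 2) |
|---|---|---|---|---|
| 0 | 16 | 0% | 20% | 8/12 |
| 2 | 12 | 25% | 15% | 6/14 |
| 4 | 8 | 50% | 10% | 4/16 |
| 6 | 4 | 75% | 5% | 2/18 |
| 8 | 0 | 100% | 0% | 0/20 |

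Phase 1b stays at 126 if D1 and D2 are each filled to 40, as 4.1.2 and 9.5 indicate, so that Stage 2 grows to 32+k. If Stage 2 is held at 32, each combination cohort reaches 40−k and Phase 1b is 126−2k.

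**How large k could be.** Protocol 4.1.1: "A 2-cycle DLT observation will apply to all cohorts in Phase 1a", which is 42 days.

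- If RP2Dm waits for completion of Phase 1a (one reading of 4.1.1.4), the window for early entry is 0 days.
- Suppose RP2Dm is set when A6 clears and both Part B levels run. In the protocol's example "Cohort B1 will only begin after the safety of dose level 6 in monotherapy dose escalation is cleared". The second combination level then waits in turn: "Cohort B2 may begin only after both Cohort A6 and Cohort B1 are complete". The window is therefore at least 42 + 42 = 84 days.
- The SAP 5.1.1 example ties B1 to dose level 5 instead. B1 may then overlap A6, which leaves at least 42 days. The two examples differ and need reconciling.

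Taking accrual of 0.5, 1 or 2 patients per cohort per 28 days (an assumption), k = rate × days/28:

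- 84 days: k = 1.5, 3, 6, giving 13, 10, 4 randomised.
- 42 days: k = 0.75, 1.5, 3, giving 14.5, 13, 10 randomised.

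**Precision.** The 95% half-width for a difference in a continuous PK/PD measure, in SD units with n per arm, is t(0.975, 2n−2) × √(2/n). At n = 8 it is 1.07, and at n = 4 it is 1.73.

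**Analysis sets at k = 0.** Each tumour type has 8 monotherapy and 40 combination patients. Randomised patients are 8 of 8 and 8 of 40, so 32 of 48 (67%) are not randomised, and nothing in the SAP separates them.

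**The case against.** The early opening looks deliberate. The protocol's summary of changes records added text on C1/C2 enrolment and randomisation, while the SAP is version 1, approved before the first patient visit. Section 6.3 and the SAP may simply not have caught up. That would explain the conflict but not remove it. It does favour a repair that keeps early accrual.

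Early entrants might be meant as additions to a full 16, with approximate totals absorbing them. The text allows some doubt, but a rule that stops at 8 accrued points the other way.

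The size is uncertain. k may be zero, the accrual rates are assumed, and the windows rest on illustrative sequences. The RP2D decisions also draw on 90-day follow-up data and could move by different amounts. All of this stands, and it limits the claim to what the plan permits.

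On (b), no between-arm estimate or formal ORR test is specified, biomarker analyses go to a separate SAP, and a Stage 1 subset could be formed later from randomisation records. These points keep the matter short of serious. They do not justify leaving the set undefined, because 9.2 calls n=16 necessary for this comparison and an analysis chosen after the data are seen carries less weight.

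Restricting to Stage 1 also widens intervals: by the same method for unequal arms, t(0.975, 46) × √(1/8 + 1/40) ≈ 0.78 SD at 8 versus 40, against 1.07 SD at 8 versus 8. Showing both summaries avoids that loss.

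**Conclusion.** Both parts hold, and the plan should be corrected. The conflict between 4.1.2 and 6.3 is plain on the text. Its effect ranges from none to loss of the whole randomised comparison, depending on a k that the documents leave open. The missing Stage 1 set does not depend on k: as planned, about 80% of the combination patients in each by-arm summary were never randomised. The consequences are confined to descriptive safety and PK/PD comparisons. No test or decision rule fails, the interim review of 20 combination patients still takes place, and pooling to 40 for antitumour activity is the intended design.

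**What to change.** 1. Reconcile protocol 4.1.2, protocol 6.3 and SAP 5.1.2, stating 8 per cohort in either case. Two routes keep Phase 1b at 126:
   - Fill C1 and C2 by randomisation only, and stop at 8 randomised monotherapy patients per cohort. No extra patients are needed, but monotherapy accrual may start later by the window above (0 to at least 84 days).
   - Keep early accrual under the present cap, flag those patients as non-randomised, amend 6.3, and restate 16 randomised and 8 from Stage 1 as maxima. This is a text change with no extra patients or delay, but the randomised set falls to 2(8−k).

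   Keeping early accrual and still randomising 16 per tumour type would also be consistent, but it raises Phase 1b to 126 + 2k (up to 142), so it is a change of sample size rather than a clarification.

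2. In SAP 5.4 and 5.4.1, separate randomised from enrolled and define a concurrently randomised Stage 1 set per tumour type. Use it for the monotherapy-versus-combination safety and PK/PD summaries. Keep the pooled by-arm summaries but label them non-randomised, and leave the n=40 antitumour estimate as planned. The cost is one flag and one extra set of summaries.
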